Title: Are Todays Continuous Glucose Monitoring Precise and Can They be Used to Reveal and Reduce Glycaemic Variability?

NCT: NCT03842683

Date: August 31th 2018

Mandatory elements to be included in access requests

Data Sharing Agreement

Please refer to the Data Sharing Agreement

Potential conflicts of interest outside the funding of the proposed research

Please refer to the Data Sharing Agreement

Funding of the proposed research

None

Research team information

[name], Senior Researcher, Steno Diabetes Center Nordjylland
[name], Head of Research at Steno Diabetes Center Nordjylland
[name], Aalborg University
[name], Head of Steno Diabetes Center Zealand

Abbreviated CV's for all team members are attached.

Research proposal information

Title of the proposed research

Are todays Continuous Glucose Monitoring precise and can they be used to reveal and reduce glycaemic variability?

Scientific rationale and relevance of the proposed research describing the objectives and the hypotheses corresponding to the objectives of the research.

Continuous Glucose Monitoring (CGM) provides an interstitial glucose reading every 5 minutes and is thus a powerful and important tool to identify glycaemic variability in people with diabetes. [1] CGM is valuable for people with diabetes to understand their glucose metabolism and it has the potential to be used for detection and prediction of glycaemic excursions, such as, the potentially fatal and inevitable events of hypoglycaemia, [2] [3] or even as a component in the holy grail of diabetes technology; the artificial pancreas. [4]

However, CGM has been criticised for being inaccurate and unreliable, amongst others, due to the physiological and a device-related delay between plasma glucose (PG) and interstitial glucose (IG). [5] [6] Nevertheless, CGM keeps on being popular and in February 2017 an international consensus was established at the Advanced Technologies & Treatments for Diabetes (ATTD) congress that even considers CGM data as a valuable and meaningful end point to be used in clinical trials of new drugs and devices for diabetes treatment where accuracy is of high importance. [7]

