The above mentioned use cases entail that the CGM data are accurate. Therefore, the first part of this research proposal is to investigate whether the newest state-of-the-art CGM devices used in Novo Nordisk trials are in fact accurate. Based on these results, it is investigated to which degree glycaemic variability can be revealed.

Short lay summary of the proposed research intended for public disclosure

Use of devices for continuous monitoring of the blood sugar is valuable for people with diabetes to understand their disease and to help prevent low blood sugar. Furthermore, continuous monitoring should be used in drug development to evaluate efficacy and safety. However, the devices have been criticised for being too inaccurate. This investigation sought to reveal the inaccuracies of current devices and to assess the subsequent usability related to the mentioned use cases.

Research methodology and data (brief description of the intended method for the use of the requested data and a detailed description of the different data sources of the data that is intended to be included)

To investigate the accuracy of CGM, mean absolute relative difference (MARD) will be calculated and presented and the impact of the delay assessed by time shifting CGM measurements. Furthermore, correlation analyses, between for example, PG and first derivative of IG, will be performed to try to understand when CGM devices tend to measure inaccurate. Lastly, machine learning and/or deep learning approaches will be utilised to reveal glycaemic patterns and to detect/predict outcomes, such as, hypoglycaemia.

Different glycaemic variability investigations will be undertaken:

- Test of PG vs IG and effect on clinical research. [analysis of differences]
- Correlation between PG values at bedtime and nocturnal hypoglycaemic events [correlation analyses]
- Effect of main evening meal and meal-time dose on nocturnal hypoglycaemic events [correlation analyses]
- Prediction of PG-confirmed hypoglycaemic events with CGM, dose and meal data as input [machine learning]
- The optimal dose and meal distribution and least CGM variability / eHbA1c [machine learning]
- Algorithm to suggest optimal dosing in relation to glycaemic variability [machine learning]

Requested data are demographic, CGM, meal, dose and hypoglycaemia data from the following trial. The analyses are independent of treatment and therefore the treatment arm can be blinded.

NN1218-3854

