APPENDIX 1: ANALYSIS PLAN

More of the investigation are of an exploratory and descriptive nature without use of treatment arm and the below information is therefore not always feasible to provide.

Endpoints: Difference between PG and IG. Number of Level 1 and 2 CGM hypoglycaemic events. Time in range of CGM and PG values. Sensitivity and specificity of different models.

Analysis Set: In an intention-to-“participate” manner all non-missing data will be used in these investigations. Imputation of missing values will in some cases be necessary, see below.

Statistical models: Difference analysis will be carried out using 2-sample t-tests or more advanced models such as ANOVA or MMRM with adjustment of sex, BMI, geographical region etc. where applicable. Machine learning approaches will include models such as Kernel SVM and neural networks with PCA, SEPCOR and forward selection for feature elimination.

Transformation of data: Transformations of data will be necessary to “fit” data into the machine learning models. For example, this will include splitting up data in training and evaluation data. If data are not normally distributed, logarithmic transformation may in most cases be performed.

Handling of missing data: Multiple imputation will be used when applicable, but for signal imputation, simpler methods will be used. For example, to get pairs of CGM and glucose meter data, linear interpolation of “missing” CGM data at the time points of glucose meter data may be applied.

Multiplicity issues: For multiple hypotheses testing simple Bonferroni corrections will be made to control the type 1 errors when applicable.

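### No rule for meter readings that may have calibrated the sensor: if the sensor was meter-calibrated, MARD, the PG-IG difference and the time-shift result can be biased, in a direction that depends on the calibration type

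*SAP*

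**What the plan says.** The protocol's first question is whether "the newest state-of-the-art CGM devices used in Novo Nordisk trials" are accurate (scientific rationale). Under research methodology, "mean absolute relative difference (MARD) will be calculated and presented", with "the impact of the delay assessed by time shifting CGM measurements". The SAP (Appendix 1, Endpoints) lists "Difference between PG and IG" first.

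Under Analysis Set, the SAP states that "all non-missing data will be used in these investigations". Under Handling of missing data it gives the only pairing method described, in which linear interpolation of absent "CGM data at the time points of glucose meter data may be applied". The protocol notes that CGM "provides an interstitial glucose reading every 5 minutes", so each interpolation spans about five minutes.

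The available text does not mention calibration. It does not say whether the sensor was calibrated by meter or in the factory, or which meter readings were used. It contains no exclusion and no sensitivity analysis on this point. The data request covers demographics, CGM, meals, doses and hypoglycaemia, and lists no calibration times or flags.

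**The concern.** An accuracy study needs a reference that is independent of the device under test. If a meter reading was entered to calibrate the sensor, the CGM trace has been adjusted towards that reading. Scoring the trace against it then measures, in part, how the sensor agrees with its own calibrator.

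The time-shift analysis is exposed in a second way. To undo a delay, it pairs each meter reading with later CGM values. Under real-time calibration, the later values are the ones already corrected. MARD can then fall on shifting because of calibration and not because interstitial glucose trails plasma glucose.

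At stake are the main results of the first part of the research: MARD, the PG-IG difference and the estimated effect of delay. More data of the same kind would not remove the bias.

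**Working it through.** The documents give no expected MARD, delay or calibration scheme, so there is no plan figure to reproduce. Every numerical setting below is an assumption, except the 5-minute interval and the linear interpolation.

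**Step 1: what interpolation does to a calibrating pair.** Let b be the sensor error just before calibration and k the share of it that calibration removes. Let w be the position of the meter time between the two neighbouring CGM readings (0 to 1). Ignore noise and suppose no true delay.

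- Real-time, correction from the next reading: the unshifted error is (1 - w)b + w(1 - k)b = b(1 - wk). If w is uniform, this averages b(1 - k/2). At a +5 min shift both neighbours are corrected and the error is b(1 - k). With k = 1 it goes from 0.5b to 0. With k = 0.5 it goes from 0.75b to 0.5b. Agreement improves on shifting although no delay exists.
- Real-time, correction taken up after 10 min: the unshifted error is the full b, so there is no flattering of unshifted MARD. The improvement appears only at shifts of about 10 min or more.
- Retrospective: the trace is pulled towards the meter value at the meter time itself. The error is b(1 - k) at shift zero, and moving either way tends to worsen it.

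On these pairs the PG-IG difference is pulled towards zero in the first and third cases.

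**Step 2: simulation.** CGM was placed on a 5-min grid and interpolated linearly at meter times, with shifts from -30 to +30 min. Sensor drift had SD 10%, sensor noise 6% and meter error 5%. Of the daily meter readings, 1 of 7, 2 of 7 or 2 of 4 were calibrations, with calibration weight 0.5 or 1. The true lag was about 0 or 10 min. Gain is unshifted MARD minus MARD at the best shift. All figures are MARD percentage points.

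| Calibration type | MARD, all pairs minus non-calibrating pairs | Gain, no lag: all v non-calibrating | Gain, 10-min lag: all v non-calibrating |
|---|---|---|---|
| Real-time, immediate uptake | -0.3 to -2.2 | 0.11-1.06 v 0.00 | 0.73-1.54 v 0.19-0.45 |
| Real-time, 10-min uptake | +0.1 to +0.9 | 0.00-1.26 v 0.00 | 0.78-2.49 v 0.27-0.49 |
| Retrospective | -0.6 to -4.7 | 0.00 v 0.00 | 0.00-0.39 v 0.27-0.49 |

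**Step 3: one cell taken apart.** MARD on all pairs is f × MARD(calibrating) + (1 - f) × MARD(non-calibrating), where f is the calibrating share. Take real-time calibration with immediate uptake, weight 1, 10-min lag and f = 2/7.

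- Unshifted: 2/7 × 6.59 + 5/7 × 11.55 = 1.88 + 8.25 = 10.13 (simulated 10.12).
- At +5 min: 2/7 × 3.52 + 5/7 × 11.24 = 1.01 + 8.03 = 9.04 (simulated 9.02).
- Gain: 2/7 × 3.07 + 5/7 × 0.31 = 0.88 + 0.22 = 1.10. About 0.88 of the 1.10 points comes from the calibrating pairs. The non-calibrating pairs alone gain 0.31.

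The same setting under retrospective calibration gives MARD 7.13 on all pairs against 10.01 on non-calibrating pairs. The best shift is 0 against +5 min, so the true delay is hidden.

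**Step 4: other settings.** A separate simulation used 2 of 4 readings as calibrations. With real-time calibration and no lag, MARD was 9.03 on all pairs against 9.62 on non-calibrating pairs. At +5 min it was 8.26 against 9.87, so shifting gave a false gain on all pairs and none on the others. With retrospective calibration MARD was 4.40 against 8.57, and with a true 8-min lag the best shift was 0 against +5 min. The directions match the table.

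**The case against.** The strongest objection is that meter calibration appears nowhere in the documents. The device is unnamed, and with a factory-calibrated sensor nothing is wrong. This stands, and it makes the point conditional. It does not remove the point, because the plan lets the reader rule out neither case.

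The quoted Analysis Set sentence could also be read as a rule about keeping participants and not about which pairs are valid. The pairing sentence is an example introduced with 'may', and Appendix 1 calls much of the work exploratory and descriptive. All of this is fair. Still, no other sentence in the available text sets aside calibrating readings, and an exploratory label does not make a reference independent. Part of the SAP was not available for review, and the protocol's own SAP section defers to the Data Sharing Agreement. The absence of a rule is therefore established only for the text at hand.

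A reader might infer that MARD is understated and that a false or inflated delay will appear. The documents do not support this. They do not say that the sensor was meter-calibrated or by which scheme, and the direction changes with the scheme. With 10-min uptake, unshifted MARD is not understated. With retrospective calibration, a true delay is reduced or hidden. A reader might also want a single multiplier for the delay effect. That would be a ratio of small MARD differences under one assumed scheme, and it should not be quoted.

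**Conclusion.** The point holds conditionally. As far as the available text shows, the plan has no safeguard against scoring the sensor partly against its own calibrator. If the sensor was meter-calibrated, at least one of the main accuracy results can be biased:

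- **Real-time calibration** tends to create or inflate an apparent delay, and may understate MARD.
- **Retrospective calibration** understates MARD and can mask a true delay.
- **No meter calibration:** no effect.

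The simulated differences in unshifted MARD run from -4.7 to +0.9 points across the three schemes. These sizes rest wholly on assumed drift, noise, meter error, calibration frequency and uptake, and are illustrative only. The mechanism and its dependence on calibration type are what to rely on. The plan sets no accuracy threshold, so whether the bias would change a conclusion cannot be judged from the documents.

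**What to change.** Add to Appendix 1:

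1. State how the sensor was calibrated. If it was not by meter, one sentence saying so closes the point.
2. Request calibration times or flags with the CGM data.
3. If it was meter-calibrated, exclude calibrating readings from the primary pairs for MARD, the PG-IG difference and the time-shift analysis. Do not interpolate CGM across a calibration. Report all pairs as a sensitivity analysis.
4. If calibrating readings cannot be identified, report results on all pairs and state that accuracy and delay cannot be separated from calibration.

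Pairing each meter reading with the last earlier CGM value is not a sound substitute. At a 5-min interval it adds 0 to 5 min of lag (2.5 min on average if meter times fall evenly) to an analysis meant to measure lag. It also fails under retrospective calibration, where earlier values are adjusted too.

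The cost is a few SAP sentences and one extra data field, which the source trial may not be able to supply. Pairs are lost: under the assumed frequencies, 1 or 2 a day per participant, or from 1/7 = 14% to 2/4 = 50% of them. The reported MARD may look less favourable.

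### The SAP allows a 2-sample t-test for plasma versus interstitial glucose, although the readings are paired within people; MMRM is optional and nothing requires a paired or participant-clustered analysis

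*SAP*

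**What the plan says.** The SAP's Appendix 1 gives one sentence on testing differences: "Difference analysis will be carried out using 2-sample t-tests or more advanced models such as ANOVA or MMRM". Adjustment for sex, BMI, region and similar covariates is left to where it applies. No rule says when MMRM must be chosen. No repeated factor, covariance structure, participant effect or paired test is named.

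Three other places show what this sentence governs and what the data look like:

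- **Target.** The SAP's endpoint list opens with "Endpoints: Difference between PG and IG". Among the protocol's six glycaemic variability investigations (Research methodology and data), the first reads "Test of PG vs IG and effect on clinical research. [analysis of differences]". Of the other five, two are labelled as correlation analyses and three as machine learning.
- **Treatment.** The protocol says: "The analyses are independent of treatment and therefore the treatment arm can be blinded".
- **Data structure.** Under Handling of missing data, the SAP interpolates CGM values "to get pairs of CGM and glucose meter data", and does so "at the time points of glucose meter data may be applied". Under Analysis Set, "all non-missing data will be used in these investigations".

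**The concern.** A 2-sample t-test assumes two independent samples of independent observations. PG and IG values matched at the same moment in the same person are not independent samples. Several matched pairs from one person are not independent observations either. An ANOVA without a participant term has the same fault.

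The two violations push the standard error in opposite directions. Ignoring the positive correlation between PG and IG makes it too large, so a real mean sensor bias can be missed. Ignoring the clustering of pairs within people makes it too small, so between-person variation in sensor bias can pass for an overall bias. The documents lack the inputs needed to say which effect wins, so a reader of the resulting p-value could not tell which way it errs. The planned Bonferroni correction changes the threshold and cannot repair a wrong standard error.

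**Working it through.** The documents give no sample size, SD, correlation, number of pairs per person or alpha, so there is no plan figure to reproduce. All inputs below are assumptions, in mmol/L where they have units:

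- glucose SD s = 3.5 (PG and IG alike)
- within-person SD of the paired difference w = 1.2 (2.0 as a check)
- between-person SD of sensor bias t = 0, 0.2, 0.5, 0.8
- pairs per person m = 10 to 400
- nominal two-sided alpha 5%
- within-person differences independent over time

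Throughout, R = SE used / true SE, and type I error = 2 × [1 − Φ(1.96 × R)].

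**1. PG and IG readings entered as two samples.** R = √(2s²/m) / √(t² + w²/m); the number of people cancels.

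Example, t = 0.5, m = 50: √(24.5/50) / √(0.25 + 1.44/50) = 0.700/0.528 = 1.326, so type I error is 0.9%.

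| Bias SD t | m = 10 | m = 50 | m = 200 | m = 400 |
|---|---|---|---|---|
| 0 | 0% | 0% | 0% | 0% |
| 0.2 | 0% | 0% | 0.2% | 2.0% |
| 0.5 | 0% | 0.9% | 17.6% | 33.5% |
| 0.8 | 0.1% | 9.3% | 39.4% | 54.5% |

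The test changes from conservative to anti-conservative at m* = (2s² − w²)/t². With 2s² − w² = 24.5 − 1.44 = 23.06, m* is 23.06/0.04 ≈ 577, 23.06/0.25 ≈ 92 and 23.06/0.64 ≈ 36 for t = 0.2, 0.5 and 0.8. With t = 0 there is no crossover. With w = 2.0 the numerator is 20.5 and the points are about 513, 82 and 32.

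Simulation (100 people, 1,500 runs) agrees: 0.9% at t = 0.5, m = 50; 18.7% at t = 0.5, m = 200; 38.5% at t = 0.8, m = 200. A one-sample t-test on person-mean differences stayed at 4.6% to 6.2% over 12 settings.

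**2. Paired differences compared between two groups of people, each reading counted as independent.** R = √[(t² + w²)/(m·t² + w²)]. Type I error is 5% at t = 0. Otherwise:

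| w | m | t = 0.2 | t = 0.5 | t = 0.8 |
|---|---|---|---|---|
| 1.2 | 10 | 7.9% | 19.9% | 31.3% |
| 1.2 | 50 | 19.9% | 49.5% | 62.5% |
| 2.0 | 10 | 6.0% | 11.3% | 19.0% |
| 2.0 | 50 | 10.8% | 32.0% | 48.2% |

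Simulation (50 people per group, 3,000 runs) at w = 1.2, m = 50 gave 19.9%, 48.0% and 62.2%. A 2-sample t-test on one value per person gave 4.2% to 5.7% over 12 settings.

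**3. Person means of PG and IG entered as two samples.** Further assumptions: 300 people, m = 50, between-person glucose SD 1.5.

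- SE used = √{2 × [1.5² + (3.5² − 1.5²)/50]/300} = √(2 × 2.45/300) = 0.128.
- True SE = √[(t² + 1.44/50)/300] = 0.0098, 0.0151, 0.0305 and 0.0472 for t = 0, 0.2, 0.5 and 0.8.
- The SE used is therefore 13.0, 8.4, 4.2 and 2.7 times too large.
- At t = 0.5 and a true difference of 0.15, the 2-sample test needs an observed difference of 1.96 × 0.128 = 0.25, which is (0.2505 − 0.15)/0.0305 = 3.3 true SEs away: power 0.05%. The one-sample test on person-mean differences has 0.15/0.0305 = 4.92 and power 99.8%.

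**Cross-check in other terms.** With PG–IG correlation ρ and intraclass correlation ICC of the paired differences, true variance / variance used = (1 − ρ)[1 + (m − 1)ICC]. At ρ = 0.9, ICC = 0 the ratio is 0.10 (type I error about 0%). At ρ = 0.8, ICC = 0.20, m = 100 it is 0.2 × 20.8 = 4.16 (34%). A paired t-test that ignores participant has ratio 20.8 in that second case (67%). Pairing alone is therefore not enough.

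**The case against.** The strongest reply is that the SAP sentence is generic. It covers an endpoint list that also includes hypoglycaemic event counts and time in range, and it never says that PG and IG enter as two independent samples. The PG–IG endpoint reads naturally as a within-pair difference, the appendix builds the pairs, and sex, BMI and region suit comparisons between groups of people. On that reading the pairing is respected and cases 1 and 3 fall away. This ambiguity is real. Case 2 remains, however: a test at reading level still ignores clustering by person. The protocol's wording, a test of PG against IG, also points to the direct comparison.

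Second, MMRM is listed and could be valid. That is correct; the fault is that an unsuitable test is named first and permitted equally, with no rule for choosing.

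Third, the figures rest wholly on assumptions, including independence over time of a person's differences. Serial correlation in sensor error would move the crossover points, so these are illustrations and not estimates.

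Fourth, the consequence is modest. The protocol's main accuracy measure, "mean absolute relative difference (MARD) will be calculated and presented", and the time-shifting analysis do not use this test. The SAP describes much of the work as exploratory and says full detail is not always feasible. This limits the weight of the point. It does not make the test valid, since the SAP still plans hypothesis tests with a multiplicity correction.

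Finally, the SAP says that much of the work, not expressly all, leaves treatment arm aside. The protocol's statement is broader, and the conclusion does not turn on the difference.

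**Conclusion.** The concern holds and should be fixed. The permitted 2-sample t-test conflicts with the paired and probably repeated data that the same appendix sets up, and nothing requires the valid alternative. Under the assumed inputs, type I error for the direct PG–IG test runs from about 0% to 54.5%, the top figure occurring only at bias SD 0.8 and 400 pairs per person. For reading-level group comparisons it reaches 62.5%. The net direction cannot be settled from the documents. The effect is confined to the p-value and confidence interval for the mean PG–IG difference and for any group comparison of it. The conclusion covers the protocol and Appendix 1. The protocol refers its statistical plan to the Data Sharing Agreement, of which nothing beyond this appendix was available.

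**What to change.** Add to Statistical models in Appendix 1:

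> PG versus IG will be analysed on within-pair differences (IG − PG, or the log ratio if skewed) with participant as the cluster, using a mixed model with a participant random intercept or an MMRM with a stated within-participant covariance. The mean difference and its 95% CI will be reported. As a simple fallback, a one-sample t-test on person-mean differences will be used. 2-sample t-tests are reserved for comparing different groups of people, using one summary value per person.

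Repeated-measures limits of agreement and a sensor effect would be useful additions but are not needed to correct this fault. The cost is a few sentences and a standard mixed-model call, with no new data. Confidence intervals may widen where there are many pairs per person.

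### Does the lack of a gap limit on CGM interpolation threaten the MARD and PG-IG results?

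*SAP*

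**What the plan says.** The Protocol (Research methodology and data) states that "mean absolute relative difference (MARD) will be calculated and presented" to investigate CGM accuracy. Its scientific rationale says that CGM "provides an interstitial glucose reading every 5 minutes". In SAP Appendix 1 the first endpoint is "Difference between PG and IG".

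Under Analysis Set, "all non-missing data will be used in these investigations", followed by "Imputation of missing values will in some cases be necessary, see below". Under Handling of missing data, multiple imputation is kept for cases where it applies, but "for signal imputation, simpler methods will be used". The example given is forming CGM-meter pairs: "linear interpolation of “missing” CGM data at the time points of glucose meter data may be applied". No maximum gap, exclusion rule or repeat analysis is attached to it.

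Appendix 1 opens by warning that much of the work is exploratory and descriptive, so that full detail cannot always be given.

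**The concern.** A pair formed inside a sensor dropout does not measure the sensor. It measures how well a straight line follows glucose between two distant readings. If such pairs were kept, that error would enter the absolute relative difference and make the device look less accurate.

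The worry is reasonable for three reasons. Device accuracy is the first question of the proposal, and the work on glycaemic variability builds on the answer. The interpolation sentence stands under missing-data handling, as an example of signal imputation. And the Analysis Set paragraph qualifies its use of non-missing data by pointing forward to imputation. Nothing in the wording expressly rules out bridging a dropout, so two analysts could in principle form different sets of pairs.

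**Working it through.** **Reading the text.** Two readings are possible.

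- *Alignment.* The CGM value is missing only in the sense that the sensor did not record at the meter's time stamp, so it is interpolated between the readings on either side. This fits the stated purpose (obtaining pairs), the inverted commas around the word missing, the tie to meter time points, and the permissive verb.
- *Bridging.* The sensor was silent for a long period and the line spans it. This fits only the placement under missing data and the forward reference from Analysis Set.

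The first reading explains more of the wording.

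**Inputs.** From the documents: a 5-minute recording interval and MARD as an accuracy measure. They give no MARD target, dropout frequency, gap length or decision threshold, so there is no planned figure to reproduce. Everything below rests on assumptions.

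- *Model A.* Plasma glucose is a log-scale sum of 40 sinusoids, mean 160 and SD about 60 mg/dL. Periods are 120-240 min (fast), 180-360 (mid) or 240-720 (slow). The sensor lags by 10 min with 8% independent noise. There is no meter error, and the meter time is uniform within the gap.
- *Model B.* Glucose is a smooth log-normal series, median 9 mmol/L, log-SD 0.38, time constant 45, 60 or 90 min. Proportional sensor error has SD 12.5% (MARD 10.0% without interpolation), independent or autocorrelated.

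**MARD (%) by length of the interpolated gap**

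| Gap (min) | A: fast / mid / slow | B, independent error: 45 / 60 / 90 | B, autocorrelated error: 45 / 60 / 90 |
|---|---|---|---|
| 5 | 11.23 / 8.58 / 6.71 | 8.5 / 8.5 / 8.5 | 10.0 / 9.9 / 10.0 |
| 10 | 11.26 / 8.58 / 6.73 | 8.3 / 8.3 / 8.3 | 9.9 / 9.9 / 9.9 |
| 30 | 11.96 / 8.81 / 6.78 | 8.7 / 8.4 / 8.2 | 10.0 / 9.8 / 9.6 |
| 60 | 17.29 / 10.90 / 7.36 | 10.9 / 9.6 / 8.7 | 11.4 / 10.3 / 9.5 |
| 120 | 33.34 / 22.24 / 12.13 | 16.6 / 13.6 / 10.9 | 16.5 / 13.9 / 11.0 |
| 240 | 38.99 / 38.89 / 27.09 | 25.6 / 21.6 / 16.7 | 25.1 / 21.7 / 16.6 |

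Even the slow case of Model A omits variation slower than 12 hours. With periods of 240-1440 min, MARD moves from 6.24% to 6.28% at a 60-minute gap, and rises by about 2.6 points at 120 min and 11 points at 240 min.

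**Added points per affected pair** = MARD at the gap minus MARD at 5 min in the same column.

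- 10 min: A 0.00 to 0.03; B -0.2 to 0.0.
- 30 min: A 0.07 (6.78 - 6.71) to 0.73 (11.96 - 11.23); B -0.4 (9.6 - 10.0) to +0.2 (8.7 - 8.5).
- 60 min: A 0.04 (6.28 - 6.24) to 6.06 (17.29 - 11.23); B -0.5 (9.5 - 10.0) to +2.4 (10.9 - 8.5).
- 120 min: A 2.6 to 22.11 (33.34 - 11.23); B 1.0 (11.0 - 10.0) to 8.1 (16.6 - 8.5).
- 240 min: A 11 to 30.31 (38.89 - 8.58); B 6.6 (16.6 - 10.0) to 17.1 (25.6 - 8.5).

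**Overall rise** = share of pairs affected × added points, over both models.

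- 1% of pairs: 120 min, 0.01 × 1.0 = 0.01 to 0.01 × 22.11 = 0.22 points; 240 min, 0.01 × 6.6 = 0.07 to 0.01 × 30.31 = 0.30.
- 5% of pairs: 120 min, 0.05 × 1.0 = 0.05 to 0.05 × 22.11 = 1.1 points; 240 min, 0.05 × 6.6 = 0.33 to 0.05 × 30.31 = 1.5.

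The fast case puts all glucose variation into 2-4 hour cycles and is an upper case.

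**Signed PG-IG difference.** In Model A (fast, mid and slow) its mean stays within 0.3 mg/dL of zero at every gap when meter timing is unrelated to glucose. Its spread widens. With 5% of pairs in 120-minute gaps, the overall SD is √(0.95 × 22.9² + 0.05 × 65.2²) = 26.7 against 22.9 mg/dL (fast, +16%), and √(0.95 × 14.2² + 0.05 × 24.9²) = 14.9 against 14.2 (slow, +5%).

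**The case for a change.** The best case for a change is that it is cheap: one sentence giving a maximum gap, a count of excluded pairs and one repeat without the limit. It would record the harmless intent if that is the intent, and prevent a real error if it is not. At 5% of pairs in four-hour gaps the overall rise could reach 1.5 points, which is not trivial for an accuracy measure. The near-zero signed difference also depends on meter timing being unrelated to glucose. In Model A, pairs with a meter value below 70 mg/dL inside 120-minute gaps have a mean CGM excess of 21.0 to 96.5 mg/dL, against 1.4 to 9.4 at 5 minutes.

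What stands is that Appendix 1 is silent on gap length, and that bridging dropouts of two hours or more would be wrong.

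The rest is weaker. No dropout share appears in the documents, so the larger figures are hypothetical. At 60 minutes even the sign depends on the model. Any particular limit would be a matter of taste: gaps up to 30 minutes change MARD by less than one point per affected pair. Exclusion has its own cost, since MARD would look too good if sensors fail more often at extreme glucose. Nor would a limit touch the one effect of ordinary alignment: with fully independent reading errors, averaging two neighbours lowers MARD from 10.0% to 8.5% in Model B; with autocorrelated error it stays at 9.9-10.0%.

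**Conclusion.** No change follows. The wording leaves a gap that analysts would fill sensibly. On its natural reading, interpolation joins adjacent 5-minute readings, and the error from bridging so short an interval is negligible in both models. The feared inflation needs an analyst to keep pairs inside dropouts of about two hours or more, and enough such pairs to matter. With 1% of pairs affected, the rise is at most about 0.3 MARD points under the most unfavourable glucose dynamics tried. No stated target or decision depends on a shift of that size, and Appendix 1 presents much of the work as exploratory.

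This rests on assumed glucose speed, sensor error and lag, and on dropout shares that the documents do not give. It concerns the text of Appendix 1; the Protocol's own SAP section refers on to the Data Sharing Agreement, which was not available. Stating the pairing rule when results are reported would be good practice, but its absence here does not make the planned analysis unsound.
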